Patients should keep the application site dry for six hours but may apply an approved moisturizing lotion (Cetaphil), provided by the Sponsor, two hours after dosing. The application site should be covered to minimize sun exposure when going outside during the day. Sunscreen at the application site may be used two hours after dosing. If excessive skin irritation occurs at the application site, the parent (after consultation with the Investigator) may switch the application site temporarily to the upper thighs.

Patients who weigh ≤ 35 kg will receive 125 mg CBD Q12H (every 12 hours) (± 2 hours); for a total daily dose of 250 mg CBD. Patients who weigh > 35 kg will receive 250 mg CBD Q12H (± 2 hours); for a total daily dose of 500 mg CBD. All patients will remain on their assigned dose through Week 6. At Week 6, if the patient has less than a 25% improvement from baseline in the ABC-C irritability subscale, the investigator may increase the dose, as follows:

- Patients who weigh ≤ 35 kg receiving a total daily dose of 250 mg CBD may increase to a daily dose of 500 mg.
Patients who weigh > 35 kg receiving a daily dose of 500 mg CBD may increase the dose to 750 mg/day.

The following questionnaires and scales will be administered at Visit 2, Visit 3, Visit 4, Visit 5, Visit 6, and Visit 7 EOS/ET, unless an exception is noted:

- ABC-C
- CGI-S
- Clinical Global Impression-Improvement (CGI-I) (not completed on Visit 2, Day 1)
- ADAMS
- C-SSRS
- Qualitative Caregiver Reported Behavioral Problems Survey (not completed at Visit 2)
- Children's Sleep Habit Questionnaire (Visit 4 and Visit 7 EOS/ET only)
- PARS-R

End of Study (EOS) / Early Termination Visit (ET):

Patients not on AEDs who are prematurely discontinued or do not qualify for Period 2, will complete the early termination procedures at Visit 4 EOS/ET.

Patients taking valproate or valproic acid for the treatment of seizures or epilepsy, including patients who prematurely discontinue, will taper their current study dose in the following manner beginning at Visit 7 EOS/ET. Should patients taking AEDs at the EOS continue to receive drug through Special Access (if available) they will not taper their dose.

- Participants who weigh 35 kg or less and were receiving 250 mg daily dose of ZYN002, will be reduced to 125 mg daily dose over one week. Only one sachet will be applied each day around the same time in the evening. After the taper, the participants will discontinue from the study at Week 40.

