7.5. Dose Adjustment Criteria

Patients will receive their assigned dose of ZYN002 as described in Section 7.4. Dose adjustments will be made for patients on AEDs for treatment of seizures or epilepsy, who will have a Taper Period at the end of the study, unless they are transitioning to receive drug through Special Access, if available (Section 7.8).

Should the weight of the patient change from visit to visit the dose may be adjusted, at the discretion of the investigator.

In addition, at Week 6 if the patient has less than a 25% improvement from baseline in the ABC-C irritability subscale, the investigator may increase the total daily dose.

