7.8. End of Study / Early Termination Visit

All patients will complete the EOS/ET Visit assessments at Week 38. Patients not taking AEDs will only have a morning dose of study drug at the Week 38 Visit before discharge from the study. The following will be completed at the EOS/ET Visit:

- Laboratory and urinalysis tests as defined in Section 7.6.15.3.
- Concomitant medication review
- Physical/neurological examination
- Vital signs
- 12-lead ECG
- Pregnancy test (females only)
- Collection and site review of patient Daily Skin Irritation Diary (diary for AED patients will also be collected Week 16 or 17)
- CBD/THC plasma sample drawn
- Valproic acid plasma sample drawn (for patients taking valproate or valproic acid)
- Skin irritation examination
- Adverse event review
- Completion of patient questionnaires and scales – refer to Table 5 and Table 6 in Section 7.7
- Study drug will be applied (last dose for patients not taking AED medication, not applicable to ET patients)

Patients not on AEDs who are prematurely discontinued will complete the early termination procedures at Visit 7 EOS/ET.

Patients taking valproate or valproic acid for treatment of seizures or epilepsy including patients who prematurely discontinue, will taper their current study dose in the following manner beginning at Visit 7 EOS/ET. Should patients taking AEDs at the EOS continue to receive drug through Special Access (if available) they will not taper their dose.

- Participants who weigh 35 kg or less and were receiving 250 mg daily dose of ZYN002, will be reduced to 125 mg daily dose over one week. Only one sachet will be applied each day around the same time in the evening. After the taper, the participants will discontinue from the study at Week 40.
 - If the participant's dose was increased at Week 6 to 500 mg daily dose of ZYN002, the dose will be reduced to 250 mg daily dose over one week with 2 sachets applied each day around the same time in the evening. After the taper, the participants will discontinue from the study at Week 40.

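### The taper schedule in protocol 7.8 names only valproate patients, although the rest of the plan gives the taper to all patients on anti-epileptic drugs (AEDs)

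*Protocol*

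**What the plan says.** The step-down doses, in sachets per day by weight and current dose, appear in protocol 7.8, in the End of Study part of the protocol synopsis, and in the synopsis reproduced in the SAP. In 7.8 the lead sentence is "Patients taking valproate or valproic acid for treatment of seizures or epilepsy including patients who prematurely discontinue, will taper their current study dose". The synopsis version is "Patients taking valproate or valproic acid for the treatment of seizures or epilepsy, including patients who prematurely discontinue, will taper", and the SAP copy matches it.

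Elsewhere the taper belongs to AED patients as a class. Section 7.5 is the clearest: "Dose adjustments will be made for patients on AEDs for treatment of seizures or epilepsy, who will have a Taper Period". It then refers the reader to 7.8 for that taper.

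The no-taper rules in 7.8 are also written by AED status, not by valproate status:

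- "Patients not taking AEDs will only have a morning dose of study drug at the Week 38 Visit before discharge from the study"
- the Week 38 application is the "last dose for patients not taking AED medication, not applicable to ET patients"
- on early discontinuation, the rule reads "Patients not on AEDs who are prematurely discontinued will complete the early termination procedures at Visit 7 EOS/ET"

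The synopsis counterpart of the last rule begins "Patients not on AEDs who are prematurely discontinued or do not qualify for Period 2".

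**The concern.** The two branches of 7.8 are not complements. One is defined by taking valproate, the other by taking no AED. Between them lies a child whose seizures are treated with a different permitted AED. Section 7.5 sends that child to 7.8 for a taper, and 7.8 then has no lead sentence that includes the child.

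What is at stake is end-of-study dosing in children with a seizure disorder. Safety is the primary objective, an increase in seizure frequency or severity is recorded as an adverse event, and the sponsor chose to taper AED patients. Whether a child receives study drug after the end-of-study visit should not depend on which section the site reads.

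**Working it through.** This is mainly a comparison of text. The arithmetic only sizes the difference between the two readings.

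**Step 1. Who tapers, by location.**

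| Location | Taper population |
|---|---|
| Protocol 7.8, lead sentence | Valproate or valproic acid |
| Protocol synopsis, End of Study | Valproate or valproic acid |
| SAP copy of the synopsis, End of Study | Valproate or valproic acid |
| Protocol synopsis, Methodology | AED patients |
| Protocol synopsis, Duration of Treatment | AED patients |
| Protocol 7.1 | AED patients treated for seizures or epilepsy |
| Protocol 7.5 | AED patients treated for seizures or epilepsy |
| Protocol Table 5, footnote a | AED patients |
| Protocol Table 6, footnote a | AED patients |
| Protocol 9.3 | AED patients |
| Protocol 9.4 (taper supply) | AED patients treated for seizures or epilepsy |
| SAP section 4 | AED patients treated for seizures or epilepsy |

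Three statements are limited to valproate. Eight protocol statements and SAP section 4 are not. The SAP also repeats the AED-wide wording in its copied synopsis and schedule footnotes, so it conflicts internally too.

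**Step 2. Can a patient fall in the gap?** Yes. Exclusion criterion 7 bars seven drugs: clobazam, phenobarbital, ethosuximide, felbamate, carbamazepine, phenytoin and vigabatrin. Section 9.2.1 permits AEDs outside the exclusion criteria. Inclusion criterion 6 asks patients with a seizure history who are on treatment only for a stable regimen of one or two AEDs. Nothing restricts AEDs to valproate.

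**Step 3. Does other text supply the missing instruction?** Only by inference. The Special Access sentence in 7.8 speaks of AED patients generally, but it only exempts those who continue the drug. The schedule tables head the taper columns with a 50% weekly reduction, without sachet counts. That heading also fails to match 7.8 for 750 mg/day: week 1 is 375 mg (a 50% cut), but week 2 is 250 mg, a cut of (375 − 250)/375 = 33%. The explicit extension of the taper to patients who discontinue early appears only in the valproate sentences.

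**Step 4. Size per affected child.** One sachet delivers 125 mg. Taper dose = 7 days × daily dose, summed over the taper weeks in 7.8; sachets = mg / 125.

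| Group and dose at end of study | Taper (mg/day) | Days | Total mg | Sachets |
|---|---|---|---|---|
| 35 kg or less, 250 mg/day | 125 | 7 | 7×125 = 875 | 7 |
| 35 kg or less, 500 mg/day | 250 | 7 | 7×250 = 1750 | 14 |
| Heavier, 500 mg/day | 250, then 125 | 14 | 1750 + 875 = 2625 | 21 |
| Heavier, 750 mg/day | 375, then 250 | 14 | 2625 + 1750 = 4375 | 35 |

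Under the narrow reading each total is zero for a child on a non-valproate AED.

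**The case against.** The best reply is that the intent is plain. Sections 7.1, 7.5, 9.3 and 9.4 and the footnotes to Tables 5 and 6 all point to AED patients. In 7.8 itself, calling Week 38 the last dose for those not on an AED implies that AED patients dose beyond it, and the Special Access exemption presupposes that AED patients otherwise taper. The dose steps depend on weight and current dose, not on which AED is taken, so a site could apply them unchanged. No text orders an abrupt stop. The Week 40/41 visit is already required for AED patients by Table 6 footnote a and by 9.3, those who leave at Week 14 return at Week 16 or 17 under Table 5 footnote a, and 9.4 already supplies taper drug. The terminal half-life of about 4 to 12 days (protocol 5.2) means exposure falls slowly anyway.

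All of this stands as mitigation, and it is why the point is minor. It does not remove the conflict: the one place with dosing instructions defines its population more narrowly than the sections that refer to it.

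A second reply is that the repair leaves a residue. Some AED-wide statements carry no seizure indication, so a child taking a permitted AED for another reason would still lie outside both lead rules of 7.8. That is true, but it is a separate ambiguity that exists now and that the edit does not worsen.

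**Conclusion.** The inconsistency is real and minor. As written, the operative taper rule omits children whose seizures are treated with a permitted AED other than valproate, while the rest of the plan includes them. For each such child the readings differ by 7 or 14 days of dosing, 875 to 4375 mg in total. How many of the approximately 20 patients this concerns is not stated; it may be none. The documents do not show clinical harm from omitting the taper. No visit, efficacy estimate or analysis population depends on the answer. The judgement that AED-wide tapering was intended is an inference from the weight of the other text and from the Special Access sentence.

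**What to change.** In the three lead sentences (protocol 7.8, protocol synopsis, SAP copy of the synopsis) replace valproate or valproic acid with AEDs, keeping the seizure or epilepsy indication. That matches protocol 7.1 and 7.5 and SAP section 4. Leave the other AED-wide statements and the no-AED rules unchanged, so that no patient loses a taper now given, and keep the valproate wording for blood sampling only.

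The cost is one phrase in three sentences, with no new visit, procedure or drug supply. SAP 5.3 estimated the last Period 2 completion as 14 November 2022, and the Note to File effective 16 February 2026 describes data collection in the past tense and says the protocol and SAP will not be updated. If dosing has ended, a short note to file stating which taper rule sites applied is enough, with the wording corrected before any reuse of the protocol text.

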 - If the participant's dose was increased at Week 6 to 500 mg daily dose of ZYN002, the dose will be reduced to 250 mg daily dose over one week with 2 sachets applied each day around the same time in the evening. After the taper, the participants will discontinue from the study at Week 40.
- Participants who weigh 35 kg or more and were receiving 500 mg daily dose of ZYN002, will be reduced over two weeks. During the first week the dose will be reduced to 125 mg two times a day (applied 12 hours apart) which will make the total daily dose 250 mg. This is one sachet in the morning and one sachet in the evening. During the second week, the dose will decrease to 125 mg daily dose, which means one sachet each day for a week applied each day around the same time in the evening. After the taper, the participants will discontinue from the study at Week 41.

If the participant's dose was increased at Week 6 to 750 mg daily dose of ZYN002, the dose will be reduced to 375 mg daily dose during the first week with one sachet applied in the morning and 2 sachets applied every evening. During the second week, the dose will decrease to 250 mg daily dose, which means 2 sachets each day for a week applied each day around the same time in the evening. After the taper, the participants will discontinue from the study at Week 41.

- Patients tapering their dose will have all Visit 4 EOS/ET assessments completed.
- At Week 38, patients will have their original dose in the morning and will have their evening dose as their new tapered dose.
- Patients will return on Week 40 or 41 and have the following assessments completed:
 - Concomitant medication review
 - Vital signs
 - Targeted physical exam if investigator deems clinically relevant
 - Pregnancy test (females only)
 - C-SSRS administered
 - Collection and review of Skin Irritation Diary
 - Skin irritation examination
 - Adverse event review

Patients having a skin irritation score > '0' at Visit 7, or Weeks 40 or 41 (for patients taking AEDs) will continue to be followed through Unscheduled Visits until the skin irritation score is recorded as '0' (no erythema).

Safety Monitoring:

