| Parent/caregiver Completes Daily Skin Irritation Diary ^j | X | X | X | X | X | X | X | |
| Review Patient Skin Irritation Diary | | X | X | | | X | X | |
| Skin Irritation Exam ^k | | X | X | | | X | X | X |
| Adverse Event Review | X | X | X | | | X | X | X |

Table 5 Footnotes - Period 1:

- a. All patients will have a Week 14 Visit/ET. All patients that do not qualify for Period 2 will have an End of Study Visit at Week 14. AED patients will taper study drug for 1 or 2 weeks after the EOS Visit and return on Week 16 or 17 for final discharge from the study.
- b. For patients that do not qualify for Period 2, Week 14/Visit 4 EOS/ET patients will have both weight and height taken. For patients taking AEDs and returning on Week 16 or 17 to be discharged from the study, a targeted physical examination (heart, lungs, abdomen and extremities) may be performed, if the investigator deems clinically relevant.
- c. Vital signs (including blood pressure, heart rate, respiratory rate, and infrared forehead or oral or tympanic temperature) will be recorded after the patient has been sitting for at least 5 minutes. Vital signs will be assessed at each study visit pre-dose.
- d. One ECG to be collected prior to starting treatment (Screening or Visit 2), provided that ECG is normal or has a finding that is not clinically significant.
- e. A pregnancy test will be completed at Week 6, and Week 14/EOS/ET for all females of childbearing potential. Pregnancy tests can be plasma or urine.
- f. Patients receiving valproate or valproic acid will have a blood sample drawn for plasma level of valproic acid. Where possible, effort should be made to get a trough sample. If not, the AED morning dose may be administered prior to the clinic visit. The time of the prior dose of study drug and valproate/valproic acid, if applicable in addition to the time of each blood sample collection will be recorded. During the Treatment Period valproic acid (for patients receiving valproate or valproic acid) blood samples will be taken at Week 6, and Week 14.
- g. On Day 1 the parent/caregiver will be instructed on how to complete the daily skin irritation diary. Scoring of skin irritation will start the evening of Day 1 through discharge from the study by the parent/caregiver. The site will evaluate the parent/caregiver applying the study treatment at each study visit and provide feedback/additional instruction as applicable.

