- h. At Weeks 6, and 14 parents/caregivers will administer the dose in the clinic after they have their PK and valproic acid (for patients taking valproate/valproic acid) blood drawn. At Week 14 patients who require a tapering period will be provided a 1 or 2-week supply of study treatment.
- i. A skin assessment examination will be completed by the Investigator at Day 1 pre-dose. Shoulders and upper arms will be examined to determine there are no skin disease or condition, including eczema, psoriasis, melanoma, acne, contact dermatitis, scarring, imperfections, lesions, tattoos, or discoloration that may affect treatment application, application site assessments, or affect absorption of the study drug where study drug could be applied.
- j. Parents/caregivers will assess the application site daily and record all irritation scores in their daily skin irritation diary, starting with the PM dose on Day 1. When irritation exists, efforts will be made to apply the gel to a non-irritated area of the upper arms/shoulders and/or right and left upper thighs. Temporary application to the upper thighs can only be used after consultation with the investigator. If the skin irritation score is greater than "2", the patient will contact the Investigator to determine if an Unscheduled Visit is required.
- k. The investigator will perform a skin irritation examination pre-dose at study Visits 3, Visit 4/EOS/ET and Unscheduled Visits. The parent/caregiver will also be asked about the patients skin irritation at the Week 10 Telephone Follow-up call.
- l. A Telephone Follow-Up will occur for those patients whose dose was increased at Week 6.

Table 6: Period 2 Schedule of Assessments – 24-Week Extension Treatment

| Study Procedures | 24-Week Treatment Period 2 Visit Schedule | | | Taper Period, If Applicable | | Study Visit Week 40 or Week 41 for AED Patients Tapering Study Drug ^a | Un-scheduled Visit(s) |
|---|--|--------------------------------------|---|--|---------------------------|---|--------------------------|
| | Visit 5 Week 22 (± 3 days) | Visit 6 Week 30 (± 3 days) | Visit 7 Week 38 EOS/ET ^a (± 3 days) | Week 39 (± 3 days) | Week 40 (± 3 days) | | |
| | Study Drug Dosing | | | Tapered 50% each week. No Study Visit | | | |
| Concomitant Medications | X | X | X | | | X | X |
| Physical/Neurological Exam ^b | | | X | | | X | |
| Vital Signs ^c | X | X | X | | | X | X |
| 12-lead ECG | | | X | | | | |
| Laboratory Tests and Urinalysis | | | X | | | | |

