- Participants who weigh 35 kg or more and were receiving 500 mg daily dose of ZYN002, will be reduced over two weeks. During the first week the dose will be reduced to 125 mg two times a day (applied 12 hours apart) which will make the total daily dose 250 mg. This is one sachet in the morning and one sachet in the evening. During the second week, the dose will decrease to 125 mg daily dose, which means one sachet each day for a week applied each day around the same time in the evening. After the taper, the participants will discontinue from the study at Week 41.

- If the participant's dose was increased at Week 6 to 750 mg daily dose of ZYN002, the dose will be reduced to 375 mg daily dose during the first week with one sachet applied in the morning and 2 sachets applied every evening. During the second week, the dose will decrease to 250 mg daily dose, which means 2 sachets each day for a week applied each day around the same time in the evening. After the taper, the participants will discontinue from the study at Week 41.
- Patients tapering their dose will have all Visit 7 EOS/ET assessments completed.
- At Week 38, patients will have their original dose in the morning and will have their evening dose as their new tapered dose.
- Patients will return at Week 40 or 41 and have the following assessments completed:
 - Concomitant medication review
 - Vital signs
 - Targeted physical exam if investigator deems clinically relevant
 - Pregnancy test (females only)
 - C-SSRS administered
 - Collection and review of Skin Irritation Diary
 - Skin irritation examination
 - Adverse event review

Patients having a skin irritation score > '0' at Week 38 will continue to be followed through Unscheduled Visits until the skin irritation score is recorded as '0' (no erythema).

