9.4. Treatment Compliance

The Investigator will keep a current and accurate inventory of all clinical supplies received from the Sponsor. Any deviations from the protocol will be recorded.

All patients will be provided with a sufficient supply of study drug during their study site visit to last until their next study visit.

All parents/caregivers will be provided with a sufficient supply of study drug for the patient during their site visit. Up to a 7-Day Replacement kit(s), containing the patient's assigned study drug, will also be supplied at each visit, as needed during the study. The Replacement kit(s) are to be returned at each study visit so that drug accountability can be performed. The Replacement

kits are to be used in situations where a visit is outside the visit window and the patient requires additional study drug prior to a visit and/or study drug is inadvertently lost/damaged/destroyed. Parents/caregivers will bring the used and unused sachets, in the baggies provided, to each visit. The site will perform drug accountability (if all sachets were completely or partially utilized) at each study visit and record compliance for the previous visit.

At Week 38, patients taking concomitant AED's for treatment of seizures or epilepsy, will be provided a one or two-week supply to complete the Tapering Period (Weeks 39 and/or Week 40), unless they are transitioning to receive drug through Special Access, if available. Patients will bring their used and unused sachets to the site at each study visit. The site will perform drug accountability (if all sachets were completely or partially utilized) at each visit and record if the patient was compliant since the last visit.

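### The text ties the AED taper to Visit 7 (Weeks 38–41) and never says it applies at Visit 4, while Table 5 tapers AED patients who leave at Week 14

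*Protocol*

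**What the plan says.** **Narrative text.** Section 7.8 has all patients complete the end-of-study visit at Week 38. It introduces the dose steps for "Patients taking valproate or valproic acid for treatment of seizures or epilepsy including patients who prematurely discontinue", who "will taper their current study dose in the following manner beginning at Visit 7 EOS/ET". The switch is dated: "At Week 38, patients will have their original dose in the morning and will have their evening dose as their new tapered dose". Discharge and the list of post-taper assessments are at Week 40 or 41. The protocol synopsis and the SAP synopsis repeat this. On supply, Section 9.4 says that at Week 38 AED patients "will be provided a one or two-week supply to complete the Tapering Period (Weeks 39 and/or Week 40". Section 9.3 puts the AED return visit at Week 40 or 41, Section 7.6.10 places the targeted examination there too, and Section 7.6.15.3 sets every patient's final visit at Week 38.

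**Schedule.** Table 5, footnote a, gives patients who do not qualify for Period 2 their final visit at Week 14, and adds: "AED patients will taper study drug for 1 or 2 weeks after the EOS Visit and return on Week 16 or 17". Footnote h adds: "At Week 14 patients who require a tapering period will be provided a 1 or 2-week supply of study treatment". The table marks Weeks 15 and 16 as the taper, under a header that cuts the dose by 50% each week. SAP Table 4 copies all of this.

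**Mixed signals.** Section 7.8 itself has the diary of AED patients collected at Week 16 or 17. The synopsis starts the taper at Visit 7 and then says: "Patients tapering their dose will have all Visit 4 EOS/ET assessments completed". The matching line in Section 7.8 says Visit 7.

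**The concern.** Entry to Period 2 requires at least a 35% improvement on ABC-C Irritability at Week 14, so some patients are expected to finish there. For such a patient on an AED, the schedule and the narrative describe different exits. A site working from Table 5 hands out taper drug at Week 14 and sees the child again at Week 16 or 17. A site working from Sections 7.8 and 9.4 finds a taper that starts at a visit this child will not have, supply issued at that visit, and a return visit 24 weeks too late.

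Safety and tolerability are the primary objective. The Table 5 return visit carries the C-SSRS, skin examination, adverse event review, vital signs and pregnancy test. If sites read the protocol differently, follow-up after stopping would differ among patients in the same position, and the report could not say which rule was followed.

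**Working it through.** There is no sample size or power figure to reproduce. The check sets the passages side by side and does simple arithmetic on weeks and doses.

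**1. Timing and coverage**

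| Item | Narrative (7.8, 9.4, synopses) | Table 5 (SAP Table 4) |
|---|---|---|
| Visit from which the taper starts | Visit 7, Week 38 | Visit 4, Week 14, if not qualifying |
| Taper drug supplied | Week 38 (9.4) | Week 14 (footnote h) |
| Taper weeks | 39 and/or 40 (9.4) | 15 and 16 |
| Return visit | Week 40 or 41 | Week 16 or 17 |
| Who tapers | Valproate or valproic acid in the dose steps; AED patients in 9.4 | AED patients |
| Dose rule | Steps by weight and current dose | 50% each week |

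**2. Are these the same taper?** Offsets from the final visit: 40 − 38 = 2 and 41 − 38 = 3 weeks in Period 2; 16 − 14 = 2 and 17 − 14 = 3 weeks in Period 1. Table 5 is therefore the Period 2 taper moved earlier by 38 − 14 = 24 weeks. The narrative never makes that move, apart from the diary line in Section 7.8.

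**3. Does any narrative sentence name the AED patient who does not qualify?** No. The synopsis sends patients who discontinue or do not qualify to Visit 4, but only those not on AEDs. The taper sentence adds premature discontinuers. The synopsis lists these separately from non-qualifiers, and the taper sentence still starts them at Visit 7.

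**4. Does the 50% header reproduce the written steps?** Weekly cut = 1 − (new daily dose / old daily dose).

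- 35 kg or less, 250 mg: 1 − 125/250 = 50%. Matches.
- 35 kg or less, 500 mg: 1 − 250/500 = 50%. Matches.
- Heavier group, 500 mg: 1 − 250/500 = 50%, then 1 − 125/250 = 50%. Matches.
- Heavier group, 750 mg: 1 − 375/750 = 50%, then 1 − 250/375 = 33%. Does not match. Halving 375 mg gives 187.5 mg, or 187.5/125 = 1.5 sachets.

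The header agrees with three of the four written regimens and departs from the fourth in week 2. Table 6 carries the same header, so this mismatch also exists at Week 38.

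**The case against.** The strongest reply is that a careful site can put the exit together. The Section 7.8 steps depend on weight and current dose, not on the visit. Section 7.5 sends AED patients who taper at the end of the study to Section 7.8, and Table 5 makes Week 14 the end of study for non-qualifiers. Section 7.8 covers premature discontinuers, who by definition stop before Week 38, so its Visit 7 label may simply mean the last visit. The protocol also says that procedures follow Tables 4 to 6, and Table 5 already schedules the supply and the return visit.

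Much of this stands, and it rules out two stronger readings. A reader might infer that an AED patient leaving at Week 14 has no dose steps at all. The documents do not support that: steps exist, Section 7.5 points to them, and Table 5 adds a weekly rule. A reader might also infer that the protocol tells sites to stop such a patient without a taper. No passage says so; that reading lets silence in Sections 7.8 and 9.4 override Table 5.

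The reply does not remove the gap. Section 7.5 leads to a section whose start, switch, return visit and assessments are all dated to Weeks 38–41, so the site must infer the shift. Falling back on the table header gives a different second week for a patient on 750 mg. For an AED other than valproate, the written steps name no one at either exit.

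**Conclusion.** The inconsistency holds as a conflict of timing and coverage: the narrative ties the taper to Visit 7 and does not extend it to Visit 4, while Table 5 requires it from Week 14. The two exits differ by one or two weeks of tapered dosing and one post-treatment safety visit. The three related conflicts (Visit 4 or Visit 7 assessments, valproate or all AEDs, and week 2 at 750 mg) also stand.

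The number of patients affected cannot be derived. The documents give neither the number on AEDs nor an expected qualifying rate, so any percentage leaving at Week 14 would be an assumption. With about 20 patients enrolled, the count may be small or zero. The point bears on patient safety and on uniform follow-up. It does not threaten the efficacy summaries. It should be corrected because the correction is specific and nearly free.

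**What to change.** Reconcile the protocol synopsis, Sections 7.5, 7.6.10, 7.6.15.3, 7.8, 9.3 and 9.4, Table 5 with its footnotes, and the SAP synopsis and SAP Table 4, so that one consistent text states:

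- who tapers (valproate or valproic acid patients, or all AED patients);
- from which final visit, Visit 4 or Visit 7, with non-qualifiers named;
- when taper drug is supplied for each exit;
- which return visit and safety assessments follow each exit;
- which visit's assessments a tapering patient completes;
- whether the table header or the written steps govern, so that the two agree at 750 mg.

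The doses and the clinical rule are for the sponsor to settle.

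The cost is a protocol clarification and a matching SAP edit; Table 5 already holds the Week 14 supply and the Week 16 or 17 visit. If conduct is complete, the study report should instead state how many AED patients left at Week 14, whether each was tapered, and whether the return visit took place.
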